7.5.4 Adverse Events Follow-Up

Follow-up of adverse events considered related or possibly related to study drugs should continue until they have returned to baseline status or stabilized or the causal relationship has been changed from related to unrelated to study drug.

7.6 STOPPING RULES

The study has no formally defined stopping rules. Data will be monitored as they accumulate and the use of the experimental therapy will cease if there is clear evidence of rivaroxaban-related adverse events or of a lack of efficacy. This decision will be at the discretion of the DSMB as per section 9.5.1.

8 STATISTIC ANALYSIS

8.1 STUDY OUTCOMES

8.1.1 Primary Outcome

The primary outcome is a combined endpoint consisting of any Rintervention , Above ankle amputation and Stenosis (RAS)²at one year The 3 components of RAS are defined as follows:

8.1.1.1 REINTERVENTION

Classified as major/minor and only considers first occurrence. Major reinterventions include placement of a new surgical bypass graft, use of thrombectomy or thrombolysis, or a major surgical revision (jump or interposition graft). Minor reinterventions include endovascular procedures without thrombectomy/thrombolysis and minor surgical revisions (patch angioplasty).

Re-interventions will be classified as target lesion revascularization (TLR), target vessel revascularization (TVR) and clinically-driven target lesion revascularization (CDTLR). TLR is defined as either repeat percutaneous or surgical revascularization for a lesion anywhere within previous treated area*. TVR is any repeat percutaneous intervention or surgical bypass of any segment of the target vessel**. CDTLR revascularization is a target lesion revascularization prompted by recurrent ipsilateral limb symptoms (intermittent claudication, critical limb ischemia) or objective imaging evidence of target lesion restenosis (i.e., most commonly with duplex ultrasonography).

*A target lesion is any lesion treated or attempted to be treated with PTA. The target lesion is the treated segment starting 5 mm proximal and ending 5 mm distal to the index procedure (stent, in most cases).

**A target vessel is the vessel that contains the target lesion. The target vessel includes the target lesion as well as the entire vessel upstream and downstream to the target lesion, including side branches (native vessel).

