8.1.2 Secondary Outcomes

1. Clinical improvement defined as cumulative improvement of 2 classes of the Rutherford scale without the need for repeated TLR in surviving patients.
2. Event-free survival
3. Overall survival
4. Target lesion revascularization (TLR) between day 1 and final visit
5. Target vessel revascularization (TVR) between day 1 and final visit
6. Peri-procedure death within 30 days
7. Cumulative rate of major adverse cardiovascular events (as defined in 8.1.2.1) between day 1 and final visit
8. Cumulative rate of major bleeding (as defined in 8.1.2.2) between day 1 and day 90.
9. Cumulative rate of minor bleeding (as defined in 8.1.2.2) between day 1 and day 90
10. Biological plausibility by measuring coagulation changes and SMC proliferation markers within 7 and 90 days based on the following markers: D-dimer, soluble CD40/44 ligands, and ERK 1/2.
11. Patency rates based on the ABI index and with an ultrasound at 6 and 12 months
12. Information about feasibility of a future study:
 - a. The total number of eligible candidates identified;

- b. The percentage of eligible patients referred to our study;
- c. The percentage of eligible patients who consent to be enrolled

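### Target vessel revascularisation counts surgery only if it is a bypass, so a patch angioplasty of the target lesion is TLR but not TVR

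*Combined protocol and SAP*

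**What the plan says.** Section 8.1.1.1 sorts reinterventions by weight (major or minor) and by class: TLR, TVR and clinically driven TLR (CDTLR).

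- TLR: "TLR is defined as either repeat percutaneous or surgical revascularization for a lesion anywhere within previous treated area".
- TVR: "TVR is any repeat percutaneous intervention or surgical bypass of any segment of the target vessel".
- Footnote on the target vessel: "The target vessel includes the target lesion as well as the entire vessel upstream and downstream to the target lesion".
- Minor procedures: "Minor reinterventions include endovascular procedures without thrombectomy/thrombolysis and minor surgical revisions (patch angioplasty".

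Section 8.1.2 lists TLR as secondary outcome 4 and, as outcome 5, "Target vessel revascularization (TVR) between day 1 and final visit". Outcome 1 also uses TLR. Sections 6.2.3 to 6.2.6 collect TLR and TVR at Day 30, Day 90, Month 6 and Month 12. The primary outcome in 8.1.1 counts any reintervention, whatever its class.

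**The concern.** A class defined on the whole vessel should contain the class defined on one part of it. The footnote puts the lesion inside the vessel, so a reader would expect every TLR to be a TVR as well. The two definitions use different procedure lists, however. TLR admits surgery without restriction, while TVR admits only bypass surgery. The section itself names a surgical reintervention that is not a bypass, so the gap can be reached with the protocol's own example.

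What is at stake is one listed secondary outcome. A coordinator or adjudicator who applies the text literally would leave some surgical reinterventions out of TVR. One who applies the anatomy would include them. The two would report different counts from the same records, and the literal count could show fewer vessel events than lesion events. The pilot is meant to inform a larger trial (section 3), so the wording could be carried forward.

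**Working it through.** The plan gives no figure to reproduce here, since no rate by class is stated. The check is to apply the definitions literally.

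**Step 1. Classify by site and procedure.** There are two sites (target lesion; rest of the target vessel) and three procedure types (percutaneous; bypass; non-bypass surgery such as patch angioplasty).

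| Site | Procedure | TLR | TVR as written | TVR if all surgery counts |
|---|---|---|---|---|
| Lesion | Percutaneous | yes | yes | yes |
| Lesion | Bypass | yes | yes | yes |
| Lesion | Non-bypass surgery | yes | **no** | yes |
| Rest of vessel | Percutaneous | no | yes | yes |
| Rest of vessel | Bypass | no | yes | yes |
| Rest of vessel | Non-bypass surgery | no | **no** | yes |

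Of the 3 TLR rows, 1 is not TVR as written. With the wider definition, 0 of 3 fall outside. These are logical cases, not event rates.

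**Step 2. When does TVR fall below TLR?** Place each participant with a reintervention in one group:

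- a: lesion, percutaneous or bypass
- b: lesion, non-bypass surgery
- c: rest of vessel, percutaneous or bypass
- d: rest of vessel, non-bypass surgery

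Then:

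- TLR = a + b
- TVR as written = a + c
- TVR with all surgery counted = a + b + c + d
- Shortfall in TVR = (a + b + c + d) − (a + c) = b + d
- TVR as written < TLR when a + c < a + b, that is, when b > c

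The undercount thus appears as soon as b + d is at least 1. The reversal needs more: non-bypass surgical TLRs must outnumber TVRs outside the lesion.

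**Step 3. Size per event.** Section 8.2 gives 40 participants in total. The allocation ratio is not stated. Assuming equal arms, 40/2 = 20, and one missed participant moves that arm's TVR proportion by 1/20 = 5 percentage points. The documents give no value for b, c or d, so no expected shortfall can be calculated.

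**Step 4. Does another section repair it?** None does. Section 8.1.2 repeats the name TVR without redefining it, and the visit lists only name it.

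**The case against.** The best defence is that the intent is plain: the footnote says that the vessel includes the lesion, and a sensible adjudicator would count every TLR as a TVR. The index treatment is balloon angioplasty with or without a stent and hybrid procedures are excluded, so surgical patching may be rare. Jump and interposition grafts, the other named surgical revisions, can be read as bypass. Section 9.5.4 also provides blinded adjudication of the primary outcome, which includes reintervention.

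Much of this stands, and it limits the weight of the point. It does not remove it. Adjudication applies definitions and does not correct them, and patch angioplasty cannot be read as bypass.

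A reader might infer more than the text supports:

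- **That CDTLR is faulty too**, because a TLR qualifies if it was "prompted by recurrent ipsilateral limb symptoms (intermittent claudication, critical limb ischemia) or objective imaging evidence of target lesion restenosis". This is an explicit and self-consistent rule. CDTLR is neither a listed outcome nor a visit item, and requiring symptoms as well would be a preference. To say that it coincides with TLR needs an unsourced premise about practice, and it treats imaging that preceded a procedure as imaging that prompted it.
- **That thrombectomy of the target vessel is lost.** The section does not call thrombectomy surgical. Its wording on minor endovascular procedures implies that thrombectomy can be endovascular, and a percutaneous one counts as TVR.
- **That open surgery in general is missed.** Bypass is open surgery and is counted. Only non-bypass surgery is left out.

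**Conclusion.** The point holds as a minor inconsistency between two definitions in 8.1.1.1. Taken literally, a non-bypass surgical reintervention of the target lesion is TLR but not TVR. Secondary outcome 5 is then undercounted for these procedures, and TVR can fall below TLR under the condition in Step 2. This rests on classing patch angioplasty of the lesion as a surgical revascularisation, the natural reading since the section lists it as a reintervention to be classified.

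The 5-point figure is the weight of one participant in an assumed arm of 20, not a predicted bias. The frequency of such procedures is unknown and may be zero. It would be wrong to conclude that the main result is at risk: the primary composite is unaffected, and so is outcome 4, because the TLR definition is already the wide one.

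**What to change.** Reword TVR in 8.1.1.1 so that it covers any repeat percutaneous or surgical revascularisation in any part of the target vessel, and add that all TLR are included. Use the same wording wherever reinterventions are classified for the case report form or adjudication. The TLR definition, the primary outcome and the visit schedule stay as they are.

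The cost is one phrase and no new visits or tests. The only effect on results is that TVR counts may rise by the non-bypass surgical cases. The change should be made before the events are classified for analysis.

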8.1.1.2 AMPUTATION

Minor and major amputations (above the ankle) differentiating below-the-knee vs. above-the-knee amputation will be collected at each follow-up visit.

8.1.1.3 RE-STENOSIS

Reported in a time-to-event fashion, defined as:

- Decrease in ABI by 0.15 (or TBI drop of 0.10) or greater as compared to post-procedure value
- Duplex ultrasound demonstrating occlusion of the graft or treated vessel
- Duplex ultrasound demonstrating critical graft stenosis (Peak Systolic Velocity \geq 300 cm/s or velocity ratio \geq 3.0)
- Angiogram, MRI or CTA demonstrating occlusion of graft or of any treated vessel, or $>$ 50% stenosis in the presence of recurrent clinical symptoms

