5.2 RANDOMIZATION

Participants will only be randomized once the surgeon has completed the PTA +/- stent . PTA will be considered successful once the target lesion is crossed with a wire and catheter and a balloon angioplasty has been successfully performed. Randomization will be conducted using a customized web-based program developed for this study. The randomization process will be initiated by the local study coordinator who will access the web-based system and enter the patient's unique identifier and confirmation of eligibility and informed consent. Specific patient allocation will then be electronically delivered, to the research pharmacy who will prepare and dispense trial medication.

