6.3.3 Duplex ultrasound arterial examination

Duplex ultrasound arterial examination will be performed at the Ottawa Civic Hospital (Diagnostic Imaging) at 30 days, 6 and 12 months as part of the routine care. The following will be recorded in the CRF : re-stenosis as defined by peak velocity flow, and the Ankle Brachial Index (ABI).

The Ankle Brachial Index(ABI) is the ratio of the blood pressure in the lower legs to the blood pressure in the arms. The ABI is calculated by dividing the systolic blood pressure at the ankle by the systolic blood pressures in the arm.

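### The only duplex velocity criterion for restenosis names a graft, so a patent but restenosed angioplasty segment meets no duplex criterion of the primary endpoint

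*Combined protocol and SAP*

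**What the plan says.** The primary outcome (section 8.1.1) is a one-year composite of reintervention, above-ankle amputation and stenosis. Section 8.1.1.3 lists four ways to meet the restenosis component:

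1. a fall from the post-procedure value of at least 0.15 in ABI, or of 0.10 in TBI;
2. "Duplex ultrasound demonstrating occlusion of the graft or treated vessel";
3. "Duplex ultrasound demonstrating critical graft stenosis", set at a peak systolic velocity of at least 300 cm/s or a velocity ratio of at least 3.0;
4. "Angiogram, MRI or CTA demonstrating occlusion of graft or of any treated vessel", or stenosis above 50% on those modalities together with recurrent symptoms.

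On the procedure, section 5.2 states: "Participants will only be randomized once the surgeon has completed the PTA +/- stent". Section 4.2 excludes hybrid procedures. Section 8.1.1.1 defines the lesion by the angioplasty: "The target lesion is the treated segment starting 5 mm proximal and ending 5 mm distal to the index procedure". The same section says "Major reinterventions include placement of a new surgical bypass graft".

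Section 6.3.3 schedules duplex "at 30 days, 6 and 12 months as part of the routine care". It has the case report form record "re-stenosis as defined by peak velocity flow, and the Ankle Brachial Index (ABI"), with no cut-off and no restriction to grafts. Under section 9.5.4 a blinded committee adjudicates the primary outcome.

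**The concern.** Criteria 2 and 4 name both sites, graft and treated vessel. Criterion 3 names one, and it is the site that the index procedure does not create. Because the adjacent lines distinguish the two sites, a literal reader cannot take graft to include an angioplastied or stented segment.

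The trial therefore schedules duplex after angioplasty and records a velocity-based restenosis finding, yet the endpoint definition has no place for that finding in the segment that was treated. The adjudicators would have two choices: set aside a finding that the case report form calls restenosis, or apply a graft cut-off to a segment the text does not extend it to. The two readings can give different event counts. Section 8.2 judges the pilot partly on a reduction in events, and section 3 uses its data to decide whether a large trial is warranted.

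**Working it through.** No plan figure has to be reproduced, since the point rests on wording. The check has three steps.

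**Step 1. Who can meet criterion 3 as worded?** The index procedure places no graft (sections 4.1 and 5.2), and hybrid procedures are excluded. A new bypass, or a jump or interposition graft, is already a major reintervention under section 8.1.1.1, so that participant has a primary event before any stenosis of the new graft. What remains is a participant with a graft that predates enrolment; section 4.2 does not exclude prior bypass. Criterion 3 is therefore nearly empty as a source of first events, but not wholly empty.

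**Step 2. Which routes are open to a patent but restenosed treated segment with no graft?**

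| Route | Open? | Condition |
|---|---|---|
| Criterion 1, ABI or TBI | Yes | The fall must reach 0.15 (ABI) or 0.10 (TBI) |
| Criterion 2, duplex occlusion | No | The segment is patent |
| Criterion 3, duplex velocity | No | Graft only |
| Criterion 4, angiogram, MRI or CTA | Yes | Above 50% and recurrent symptoms; no visit schedules these modalities |
| Reintervention (8.1.1.1) | Yes | A procedure must be done; imaging evidence of restenosis may prompt a clinically driven revascularization |

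Neither of the two duplex criteria applies. The case that is missed is a stenosis shown by duplex velocity with no qualifying ABI or TBI fall, no symptomatic stenosis above 50% on other imaging, and no reintervention.

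**Step 3. Does another section supply the missing rule?** Section 6.3.3 refers to velocity without a threshold. Section 8.1.1.1 mentions duplex evidence of restenosis at the target lesion, as a prompt for revascularization, without a threshold. Secondary outcome 11 (section 8.1.2) reports ultrasound patency without a threshold and adds no primary event. The 300 cm/s and 3.0 values in criterion 3 are the only velocity cut-offs in the documents, and no text applies them to the treated segment.

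**The case against.** The strongest reply is that this is a drafting slip whose meaning is plain. It is the only velocity criterion in an angioplasty trial, section 6.3.3 defines duplex restenosis by velocity, and an expert blinded committee would read it sensibly. The other routes also cover part of the gap: ABI is collected at the same three visits as duplex, and a duplex finding can lead to a revascularization that counts.

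Much of this stands. The intent was probably to cover treated segments, and the gap lies in the duplex criteria, not in the endpoint as a whole. But evident intent does not alter the written rule, and it does not say whether the graft cut-off was meant for a native or stented segment.

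A second reply is that sections 8.1.1 and 8.2 cite the same paper, on performance goals for catheter-based treatment of critical limb ischemia, for the endpoint and for the 54% rate. Widening criterion 3 could therefore separate the endpoint from its planning rate. The documents do not show which definition underlies the 54%, so this stands as something to check when the wording is changed.

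Two stronger readings are tempting and are not supported:

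- A reader might infer that, since stenosis above 50% qualifies a vessel for entry, its recurrence on duplex should count by itself. Criterion 4 counts stenosis above 50% only with symptoms, and nothing in the documents equates the velocity cut-off with 50%.
- A reader might size the problem from the primary patency of about 40-60% at one year in section 1.1. For 40 participants that is (1 - 0.60) × 40 = 16 to (1 - 0.40) × 40 = 24 losing patency. That figure includes re-occlusions, which criterion 2 already counts, and ignores the other routes. Its upper end also exceeds the 0.54 × 40 = 21.6 primary events that section 8.2 expects from all components together. It does not measure how many participants depend on this wording.

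**Conclusion.** The point holds as a wording error in the primary endpoint. Followed literally, criterion 3 does not count velocity-defined restenosis in an ungrafted treated segment, and that conflicts with what section 6.3.3 has recorded as restenosis.

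Its size cannot be stated. The documents give neither the share of restenosis that would be seen only on duplex velocity nor the overlap with the other criteria, and the number of participants affected may be small.

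A reader might infer a bias between arms or a loss of power. The documents do not support either: the same definition and blinded adjudication apply to both arms, and any power figure would need an invented share of missed events. The conclusion rests on the text alone and on reading graft in its ordinary sense, as the neighbouring criteria do. It is worth correcting because it concerns a primary component and the correction is cheap.

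**What to change.** Reword criterion 3 in section 8.1.1.3 so that it covers stenosis of the treated segment, using the target lesion already defined in section 8.1.1.1, or of a graft. The sponsor should confirm which velocity cut-off is intended for the treated segment; the documents do not allow a reviewer to judge whether the graft values suit it. The sponsor should also check that the 54% rate in section 8.2 rests on the same definition. Section 6.3.3 should then refer to the same criterion, so that the case report form and the endpoint agree.

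This should be done before outcomes are adjudicated. The cost is a wording amendment to sections 8.1.1.3 and 6.3.3 with ethics board approval under section 9.2.1, plus the check of the planning rate. Duplex is already scheduled as routine care, so no new procedure, visit or participant is needed.

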8.1.2 Secondary Outcomes

1. Clinical improvement defined as cumulative improvement of 2 classes of the Rutherford scale without the need for repeated TLR in surviving patients.
2. Event-free survival
3. Overall survival
4. Target lesion revascularization (TLR) between day 1 and final visit
5. Target vessel revascularization (TVR) between day 1 and final visit
6. Peri-procedure death within 30 days
7. Cumulative rate of major adverse cardiovascular events (as defined in 8.1.2.1) between day 1 and final visit
8. Cumulative rate of major bleeding (as defined in 8.1.2.2) between day 1 and day 90.
9. Cumulative rate of minor bleeding (as defined in 8.1.2.2) between day 1 and day 90
10. Biological plausibility by measuring coagulation changes and SMC proliferation markers within 7 and 90 days based on the following markers: D-dimer, soluble CD40/44 ligands, and ERK 1/2.
11. Patency rates based on the ABI index and with an ultrasound at 6 and 12 months
12. Information about feasibility of a future study:
 - a. The total number of eligible candidates identified;

- b. The percentage of eligible patients referred to our study;
- c. The percentage of eligible patients who consent to be enrolled

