Design:	This is a pilot study conducted at one center, The Ottawa Hospital. It is a Phase 2 open label randomized controlled trial. Consenting participants, meeting all eligibility criteria will be randomized, post PTA procedure, to one of two groups: Rivaroxaban 2.5 mg BID X 90 days plus ASA 81 mg daily OR Clopidogrel 75 mg daily X 90 days plus ASA 81 mg daily Participants will have study drug dispensed at Day 1 and take medication for 90 days. ASA may be continued after the study, for both groups, as per the standard of care. Visits will occur at 7 days, 30 days, 90 days, 6 months and 12 months. Participants will be followed for 12 months (\pm 14 days) in total. Adverse events will be collected for the first 90 days .
Intervention Description:	Treatment Arm 1 Rivaroxaban 2.5 mg twice daily for 90 days (rivaroxaban will be started 6 to 8 hours after the finalization of the procedure) and 325mg of ASA on day 1 then 81 mg of ASA daily for 89 days Treatment Arm 2 Clopidogrel 300mg on Day 1 (loading dose) then 75 mg daily for 89 days and 325mg of ASA on Day 1, then 81 mg of ASA daily for 89 days
Number of participants:	40

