1 STUDY RATIONALE AND BACKGROUND

1.1 CRITICAL LIMB ISCHEMIA (CLI)

Peripheral arterial disease (PAD) affects over 27 million people in the industrialized world, and is associated with significant morbidity and mortality¹. Up to 10% of patients with PAD² will develop critical limb ischemia (CLI) presenting as resting pain, ulcers, gangrene, and limb loss^{1;3;4}. The typical prognosis of CLI is poor. Within 3 months of onset, 12% of patients will require an amputation and 9% will die; by one year the mortality rate is 22%². With rates surpassing those of patients with coronary artery disease (CAD), patients with CLI are also at high risk of stroke, acute coronary syndrome (ACS), and cardiovascular (CV) death^{5;6}.

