6 STUDY PROCEDURES AND EVALUATIONS

6.1 STUDY VISITS

All participants will be followed for 12 months following their angioplasty. Participants will return to The Ottawa Hospital or will be evaluated as an inpatient at 7 days. There are follow up visits at 30 days, 90 days, 6 months, and 12 months post randomization. All primary and secondary outcome data will be collected during the trial (7 days, 30 days, 90 days, 6 months and 12 months) so that procedures can be evaluated and optimized for future studies. The schedule of study events is summarized in a table in appendix 1.

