6.3 OUTCOME MEASURES

6.3.1 Rutherford scale

Participants will be evaluated according to Rutherford scale at screening, and at the day 30, month 6 and month 12 follow-up visits.

Classes in the Rutherford scale are defined as:

- Stage 0 – Asymptomatic
- Stage 1 – Mild claudication
- Stage 2 – Moderate claudication – The distance that delineates mild, moderate and severe claudication is not specified in the Rutherford classification, but is mentioned in the Fontaine classification as 200 meters.
- Stage 3 – Severe claudication
- Stage 4 – Rest pain
- Stage 5 – Ischemic ulceration not exceeding ulcer of the digits of the foot
- Stage 6 – Severe ischemic ulcers or frank gangrene

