8.2 SAMPLE SIZE CALCULATION

Based on recent data published by Conte et al² we expect that during 1 year of follow up, 54% of participants will experience the primary outcome. A total sample of 40 participants was selected and is within the recommended approach for pilot studies evaluating effects when no prior information upon which to base the sample size is available. This sample size will allow us to detect an absolute 20% reduction in the main clinical outcome with a single sided alpha of 0.2 and power of 0.6 as recommended for pilots studies⁵⁹⁻⁶¹. The study will be considered successful if we can demonstrate a reduction in events in the intervention group supported by changes in biomarkers levels (biological plausibility).

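### Secondary outcome 1 measures clinical improvement among survivors, so deaths most naturally leave the denominator and the arms are compared in groups selected after randomisation

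*Combined protocol and SAP*

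**What the plan says.** Section 8.1.2, item 1, reads: "Clinical improvement defined as cumulative improvement of 2 classes of the Rutherford scale without the need for repeated TLR in surviving patients". The words at issue are "without the need for repeated TLR in surviving patients". The item names no denominator and no visit. Section 6.3.1 sets several possible visits: "Participants will be evaluated according to Rutherford scale at screening, and at the day 30, month 6 and month 12 follow-up visits".

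Section 8.3 names the tests (Fisher's exact test for proportions) but no analysis set. Section 9.4 leaves data still missing after queries to the statistician's coding and gives no rule for deaths. Overall survival, event-free survival and death within 30 days are separate items in 8.1.2. None is combined with clinical improvement.

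On mortality, section 1.1 says of CLI: "Within 3 months of onset, 12% of patients will require an amputation and 9% will die", and "by one year the mortality rate is 22" per cent. On size and follow-up, section 8.2 says "A total sample of 40 participants was selected" and section 6.1 says "All participants will be followed for 12 months following their angioplasty". The synopsis says that participants "will be randomized, post PTA procedure, to one of two groups", without giving the allocation ratio.

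**The concern.** Randomisation makes the arms comparable at day 1. A rate computed only in those still alive at a later visit compares whoever remains, and treatment may influence who remains. The protocol gives reason to expect such influence. Section 1.4 cites a 32% reduction in all-cause death against placebo for the rivaroxaban regimen in another population. Section 2 hypothesises fewer major cardiovascular events, and section 8.1.2.1 includes vascular death among these.

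The distortion could run against either arm. If rivaroxaban kept alive patients who do not improve, they would enter its denominator and lower its rate.

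This is the first-listed secondary outcome and the only one built on the Rutherford scale. Under section 9.3 the steering committee reviews the trial's outcomes to judge whether a full trial is justified. With about 20 patients per arm, a few deaths can move the reported percentage by an amount that might be read as a signal.

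**Working it through.** The plan makes no calculation for this outcome, so there is no figure to reproduce. The 22% is a literature value and was checked only as a quotation.

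**Inputs**
- Total sample: 40 (section 8.2). Allocation ratio not stated; 20 per arm assumed.
- One-year mortality: 22% for CLI (section 1.1). Assumed alternatives: 10% and 5%.
- Improvers: no rate is given. Assumed 9 per arm, that is 9/20 = 45% of all randomised.

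**Step 1. Expected deaths per arm**, 20 × mortality: 20 × 0.22 = 4.4; 20 × 0.10 = 2; 20 × 0.05 = 1.

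**Step 2. The two rates.** Survivor-only rate = improvers / (20 − deaths). All-randomised rate = improvers / 20.

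| Deaths (A v B) | Improvers (A v B) | Survivors only | All randomised |
|---|---|---|---|
| 3 v 6 | 9 v 9 | 9/17 = 52.9% v 9/14 = 64.3% | 45% v 45% |
| 1 v 3 | 9 v 9 | 9/19 = 47.4% v 9/17 = 52.9% | 45% v 45% |
| 3 v 6 | 10 v 9 | 10/17 = 58.8% v 9/14 = 64.3% | 50% v 45% |

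The first two rows show apparent advantages of about 11 and 6 points for the arm with more deaths, although improvers are equal. In the third row the ordering reverses: arm B has fewer improvers and more deaths, yet the higher survivor-only rate. Holding the number of improvers fixed while deaths differ amounts to assuming that the extra deaths fall on patients who would not have improved.

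**Step 3. The opposite assumption.** Let deaths be unrelated to improvement, with 50% improving if alive and mortality of 30% v 14% (mean 22%). Survivor-only rates are 50% v 50%. Of all randomised, 0.50 × 0.70 = 35% v 0.50 × 0.86 = 43% are alive and improved. The survivor-only rate does not show the difference.

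**Step 4. Chance imbalance.** With deaths in each arm independent Binomial(20, m) and the same m in both, P(|D_A − D_B| ≥ 3) is:
- m = 22%: 0.34
- m = 10%: 0.18
- m = 5%: 0.07

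These probabilities go with the 3 v 6 rows. They do not apply to larger gaps: a difference of 4 or more deaths at 22% has probability 0.18. They describe chance alone, not a treatment effect on survival.

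**The case against.** **The wording has another reading.** A success could mean a patient who is alive, free of repeat TLR and improved, so that deaths already count as failures. The documents do not exclude this. It is the less natural reading, because the phrase describes the patients in whom improvement is measured and no section names all randomised participants as the denominator. If it is what the sponsor means, saying so costs nothing.

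**The 22% may not describe this trial.** It is given for CLI, whereas section 4.1 admits Rutherford category 1 and above, and section 6.3.1 labels stage 1 as mild claudication. Section 4.2 also excludes patients with a life expectancy under six months from severe concomitant disease. This stands, and is why the working gives a range.

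**The direction is not established.** A reader might infer that deaths necessarily raise the improvement rate because the sickest patients would not have improved. The documents do not support that. On the scale in section 6.3.1 a stage 1 patient cannot gain two classes, while stages 4 to 6 have the most room to improve. The percentage gaps in the first two rows of Step 2 are therefore conditional. What survives without that assumption is that a survivor-only rate fails to register excess mortality.

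**Deaths are visible elsewhere.** Overall survival is a separate outcome, so an imbalance would be seen. Seeing it does not correct this proportion. An all-randomised rate would also move with chance differences in deaths, but it would count them as failures rather than remove them.

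**Conclusion.** The point holds as a defect of definition in one secondary outcome. As most naturally read, item 1 conditions a randomised comparison on survival, and no other section says how deaths are counted. With 20 per arm and 9 improvers in each, the illustrated distortion is about 11 points for a difference of three deaths (3 v 6) and about 6 points for a difference of two (1 v 3), provided the extra deaths fall on patients who would not have improved. If deaths are unrelated to improvement, the measure is instead blind to excess mortality. The arm sizes and improver counts are assumptions, and mortality may well be below 22%.

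Two stronger readings should be avoided. A reader might conclude that the result is bound to favour the arm with more deaths; that depends on which patients die, which the documents do not say. A reader might also conclude that the trial's success criterion is compromised. It is not: section 8.2 rests success on fewer events in the intervention group supported by biomarker changes, and Rutherford improvement plays no part in it.

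**What to change.** In section 8.1.2, item 1, state that clinical improvement is analysed in all randomised participants at a named visit, for example month 12, and that death or repeat TLR before that visit counts as not improved. Naming the visit matters: without it, a patient who improves by day 30 and dies in month 11 cannot be classified. Keep the survivor-only rate as a descriptive figure, shown beside the number of deaths in each arm.

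The current definition is silent on major amputation. Whether it also counts as not improved is for the sponsor to decide and state.

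The cost is a short change of wording. Deaths, TLR, amputations and Rutherford class are already collected, so no new data are needed. The downside is a lower headline improvement rate.
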